## 6.4. WINDOWING CONVENTIONS

Unless other specified, visit data as recorded in the database will be used for the analysis. No visit windowing recalculation will be performed for this trial.

## 6.5. STATISTICAL TESTS

No formal hypothesis testing will be performed. The analysis of the data will be performed descriptively. If confidence intervals or p-values are presented, they will be interpreted in an exploratory fashion only. In this case, the default significant level will be (5%); confidence intervals will be 95% and all tests will be two-sided, unless otherwise specified in the description of the analyses.

## 6.6. COMMON CALCULATIONS

For quantitative measurements, change from baseline will be calculated as:

- Test Value at Visit X – Baseline Value

## 6.7. SOFTWARE VERSION

All analyses will be conducted using SAS version 9.4 or higher.

---

Document: \\ieedc-nas01a\BIOSdata\Boehringer\_Ingelheim\BI\_695501\NVA96235\Biostatistics\Documentation\SAP\10  
v1.0\BI\_1297.3\_SAP\_22JUN2016\_v1.0

Author: Version Number: 1.0  
Version Date: 22JUN2016

Template No: CS\_TP\_BS016 – Revision 3  
Effective Date: 01May2012

Reference: CS\_WI\_BS005

## 7. STATISTICAL CONSIDERATIONS

### 7.1. ADJUSTMENTS FOR COVARIATES AND FACTORS TO BE INCLUDED IN ANALYSES

No covariates adjustment is required in this trial.

### 7.2. MULTICENTER STUDIES

This trial will be conducted by multiple investigators at multiple centers internationally depending on the inclusions of trial 1297.2. No specific analyses based on (pooled) centers are planned.

Geographic region will be categorized using country information as follows:

Geographic Region	Country
Asia	Republic of Korea, Malaysia, New Zealand, Thailand
Europe (EU)	Bulgaria, Estonia, Germany, Hungary, Poland, Russian Federation, Serbia, Spain, Ukraine
Latin America	Chile
United States of America	United States

### 7.3. MISSING DATA

Missing safety data will not be imputed, unless otherwise specified in section 16.

Missing efficacy data will be handled as described in section 15.2.2 of this analysis plan.

For duration of disease and birth date, the missing date will not be imputed. Calculation for the partial date is described in APPENDIX 2.

### 7.4. MULTIPLE COMPARISONS/ MULTIPLICITY

No multiplicity consideration is required in this trial.

---

Document: \\ieedc-nas01a\BIOSdata\Boehringer\_Ingelheim\BI\_695501\NVA96235\Biostatistics\Documentation\SAP\10  
v1.0\BI\_1297.3\_SAP\_22JUN2016\_v1.0

Author: Version Number: 1.0  
Version Date: 22JUN2016

Template No: CS\_TP\_BS016 – Revision 3  
Effective Date: 01May2012

Reference: CS\_WI\_BS005

---

## 7.5. EXAMINATION OF SUBGROUPS

No subgroup analysis is required in this trial.

## 8. OUTPUT PRESENTATIONS

APPENDIX 1 shows conventions for presentation of data in outputs, unless other specified within the document (e.g. plasma concentration). In particular, for presentation of results, three groups of patients will be created depending on treatments assigned in Trial 1297.2.

The templates provided with this SAP describe the presentations for this trial and therefore the format and content of the summary tables, figures and listings to be provided by Biostatistics.

## 9. DISPOSITION AND WITHDRAWALS

All subjects who provide informed consent will be accounted for in this trial.

The counts of the analysis sets will be presented:

- All Subject Enrolled (ENR)
- All Subjects Assigned (ASD)
- Safety Analysis Set (SAF)
- Full Analysis Set (FAS)
- Pharmacokinetic Full Analysis Set (PKFS)

The following subject disposition and withdrawals will be presented for the ENR set:

- Screened
- Screen failure (defined as subjects who do not enter the trial and are not assigned treatment), reason for non-inclusion
- Assigned to treatment
- Assigned to treatment but not treated
- Treated
- Completed treatment

---

Document: \\jeedc-nas01a\BIOSdata\Boehringer\_Ingelheim\BI\_695501\NVA96235\Biostatistics\Documentation\SAP\10  
v1.0\BI\_1297.3\_SAP\_22JUN2016\_v1.0

Author: Version Number: 1.0  
Version Date: 22JUN2016

Template No: CS\_TP\_BS016 – Revision 3  
Effective Date: 01May2012

Reference: CS\_WI\_BS005

- Completed trial
- Discontinued from treatment, reason for premature discontinuation from treatment
- Discontinued from trial, reason for premature discontinuation from trial
- Discontinued from safety follow-up, reason for premature discontinuation from safety follow-up

Subjects enrolment will also be summarized by country and by age group (18-64, 65-84, >=85).

## 9.1. IMPORTANT PROTOCOL DEVIATIONS

Important protocol violations defined below will be listed for the ASD set:

- Trial drug not administered at all
- Severe violation of treatment compliance
  - Medical team will review subjects with treatment compliance outside 80% and 120% (refer to section 14.1) and decide if the violation is severe.
- Any deviation of inclusion/exclusion criteria should be considered as important violations.
- A severe violation to the restricted DMARD therapy (protocol table 4.2.2.1:1), as assessed by the medical team.

## 10. DEMOGRAPHIC AND OTHER BASELINE CHARACTERISTICS

No statistical testing will be carried out for demographic or other baseline characteristics.

The following demographic characteristics will be reported for ASD, FAS, SAF and PKFS:

- Age (years) at Inform Consent
- Age groups at Informed Consent
  - Adolescent (12-17 years): 12 <= AGE < 18 – no patient expected
  - Adults (18-64 years): 18 <= AGE < 65
  - Adults (65-84 years): 65 <= AGE < 85
  - Adults (Over 85 years): 85 <= AGE – no patient expected

---

Document: \\ieedc-nas01a\BIOSdata\Boehringer\_Ingelheim\BI\_695501\NVA96235\Biostatistics\Documentation\SAP\10  
v1.0\BI\_1297.3\_SAP\_22JUN2016\_v1.0

Author: Version Number: 1.0  
Version Date: 22JUN2016

Template No: CS\_TP\_BS016 – Revision 3  
Effective Date: 01May2012

Reference: CS\_WI\_BS005

- First age subgroup at Informed Consent
  - AGE < 65 years
  - AGE >= 65 years
- Second age subgroup at Informed Consent
  - AGE < 65 years
  - 65 <= AGE < 76
  - 76 <= AGE < 85
  - AGE >= 85
- Gender (Male/Female)
- Childbearing potential (Post-Menopausal / Surgically Sterile / Childbearing Potential (includes tubal ligation))
- Race (American Indian or Alaska Native / Asian / Black or African American / Native Hawaiian or Other Pacific Islander / White / Other)
- Ethnicity (Hispanic or Latino / Not Hispanic or Latino / Not reported)
- Height at baseline (cm)
- Weight at baseline (kg)
- BMI at baseline (kg/m^2)
- Country (please refer to section 7.2)
- Region (please refer to section 7.2)

The following baseline disease characteristics will be presented for FAS and SAF:

- Duration of rheumatoid arthritis (years) at Informed Consent.
- Individual parameters of ACR improvement criteria at baseline:

1. Swollen joint counts (66 joints) at baseline

Document: \\ieedc-nas01a\BIOSdata\Boehringer\_Ingelheim\BI\_695501\NVA96235\Biostatistics\Documentation\SAP\10  
v1.0\BI\_1297.3\_SAP\_22JUN2016\_v1.0

Author: Version Number: 1.0  
Version Date: 22JUN2016

Template No: CS\_TP\_BS016 – Revision 3  
Effective Date: 01May2012

Reference: CS\_WI\_BS005

---

- 2. Tender joint counts (68 joints) at baseline
- 3. Patient's assessment of pain at baseline
- 4. Patient's global assessment of disease activity at baseline
- 5. Physician's global assessment of disease activity at baseline
- 6. Patient's assessment of physical function, as measured by the HAQ-DI, at baseline
- 7. C-reactive protein (CRP) at baseline

- Erythrocyte sedimentation rate (ESR) at baseline
- Disease Activity Score 28-Erythrocyte sedimentation rate (DAS28-ESR) at baseline
- Disease Activity Score 28-Erythrocyte sedimentation rate (DAS28-CRP) at baseline

Other baseline characteristics will be presented on FAS, and SAF:

- Immunogenicity (proportion of subjects with positive ADAs result) at baseline
- Neutralizing anti-drug antibodies results at baseline
- Infection screen (for hepatitis B, hepatitis C, HIV test)
- Tuberculosis (TB) test
- Rheumatoid factor (RF) and anti-CCP antibodies

Accountability for missing data will be displayed in case of any missing entries.

## 10.1. DERIVATIONS

- Age (years) = (date of consent– date of birth)/365.25
- BMI (kg/ m^2) = weight (kg)/ height (m)
- Duration of rheumatoid arthritis (years) = (date of informed consent - date of first diagnosis + 1)/365.25
- Joint counts:
  - Swollen joint counts (66 joints)
  - Tender joint counts (68 joints)

---

Document: \\ieedc-nas01a\BIOSdata\Boehringer\_Ingelheim\BI\_695501\NVA96235\Biostatistics\Documentation\SAP\10  
v1.0\BI\_1297.3\_SAP\_22JUN2016\_v1.0

Author: Version Number: 1.0  
Version Date: 22JUN2016

Template No: CS\_TP\_BS016 – Revision 3  
Effective Date: 01May2012

Reference: CS\_WI\_BS005

Refer to section 15.2.1.2 for further calculation details

- DAS28
  - DAS28 (CRP) =  $0.56*\sqrt{TJC28} + 0.28*\sqrt{SJC28} + 0.014*GH + 0.36*\ln(CRP+1) + 0.96$
  - DAS28 (ESR) =  $0.56*\sqrt{TJC28} + 0.28*\sqrt{SJC28} + 0.70*\ln(ESR) + 0.014*(GH)$

Where:

TJC28 = 28 joint count for tenderness

SJC28 = 28 joint count for swelling

$\ln(CRP)$  = natural logarithm of CRP

$\ln(ESR)$  = natural logarithm of ESR

GH = the General Health component of the DAS, which is the patient's global assessment of disease activity.

ESR local value will be used for the DAS28 (ESR) calculation.

The following 28 joints will be evaluated for swelling and tenderness based on the eCRF entry

- 8 proximal interphalangeal (PIP) joints of the fingers (eCRF: right and left PIP2, PIP3, PIP4, PIP5)
- the interphalangeal (IP) joints of the thumbs (eCRF: right and left IP thumb)
- the 10 metacarpophalangeal (MCP) joints (eCRF: right and left MCP 1 – MCP 5)
- the wrists (eCRF: right and left wrist)
- elbows (eCRF: right and left elbow)
- shoulders (eCRF: right and left shoulder)
- knees (eCRF: right and left knee)

In determining the TJC28 and SJC28, if a joint evaluation is missing or 'Not done' at baseline (please refer to section 6.2 for baseline definition), it will not contribute to the joint counts at baseline and all subsequent visits (i.e., will be treated as 'Not Done'). If at least half but not all joints are evaluable (at least 14 joints for the 28 joint count with eCRF values 'present' or 'absent'), then the observed prorated tender/swollen joint count will be calculated. The prorated scores will be adjusted based upon the number of evaluable joints: the counted score will be multiplied by 28 and divided by the number of joints evaluated. For example, if only 25 of the 28 joints are assessed at a visit and 8 of those 25 are tender/swollen (eCRF value 'present'), the prorated joint count is  $8/25 \times 28 = 8.96$ . This value, 8.96 (not 8) will be used for DAS28 (ESR) score calculation. If less than half of the joints are evaluable (eCRF value 'not done' or missing), the number of tender/swollen joints is missing.

The General Health component of the DAS28(ESR) is Patient's global assessment of disease activity visual analysis scale (VAS) as collected in the eCRF and the ESR values provided by the local laboratory will be used for the

---

Document: \\ieedc-nas01a\BIOSdata\Boehringer\_Ingelheim\BI\_695501\NVA96235\Biostatistics\Documentation\SAP\10  
 v1.0\BI\_1297.3\_SAP\_22JUN2016\_v1.0

Author: Version Number: 1.0  
 Version Date: 22JUN2016

Template No: CS\_TP\_BS016 – Revision 3  
 Effective Date: 01May2012

Reference: CS\_WI\_BS005

---

DAS28(ESR) calculation.

In the situation where the diagnosis date is partial or missing, the corresponding durations will be presented based on the imputations specified in APPENDIX 2.

## 11. SURGICAL AND MEDICAL HISTORY

Surgical and Medical History information will be presented for the SAF. Medical History conditions are defined as those conditions which stop prior to or at Screening.

The system organ classes will be sorted by internationally agreed European Medicines Agency System Organ Class (EMA SOC) order (refer to APPENDIX 3), preferred terms (PT) will be sorted by decreasing frequencies (within system organ class).

Data captured on the “Medical and surgical history” page of the eCRF and on the “Concomitant Surgical Procedures” page of the eCRF will be merged together and assigned to prior, concomitant, or post-treatment phase.

Surgical and Medical History will be coded using MedDRA version 18.1 or higher.

See APPENDIX 2 for handling of partial dates for medical history, surgeries and procedures; if it is not possible to define an history, surgery or procedure as prior, concomitant, or post-treatment, it will be classified by the worst case; i.e. concomitant.

- Prior medical history, surgeries and procedures are defined as those conditions or procedures which stop prior to or at Screening (prior only).
- Concomitant medical history, surgeries and procedures are defined as those conditions or procedure which:
  - started prior to or at Screening and are ongoing or active at the date of Screening or
  - started after Screening during the treatment period (prior and concomitant).

Prior and concomitant surgical and medical history will be presented by SOC and PT in two separate tables.

## 12. MEDICATIONS

Medications will be presented for the SAF and coded using WHO Drug Dictionary version SEP2015 or higher.

No ATC class coding will be performed.

The medical terms will be summarized by generic medication name.

The generic medication name will be sorted by decreasing frequencies.

See APPENDIX 2 for handling of partial dates for medications; if it is not possible to define a medication as prior,

---

Document:	\ieedc-nas01a\BIOSdata\Boehringer_Ingelheim\BI_695501\NVA96235\Biostatistics\Documentation\SAP\10\		
v1.0\BI_1297.3_SAP_22JUN2016_v1.0	Author:	Version Number:	1.0
		Version Date:	22JUN2016
Template No: CS_TP_BS016 – Revision 3	Reference: CS_WI_BS005		
Effective Date: 01May2012			
Copyright © 2012	. All rights reserved.		
The contents of this document are confidential and proprietary to	Unauthorized use, disclosure or		
reproduction is strictly prohibited.			

---

concomitant, or post treatment, the medication will be classified by the worst case; i.e. concomitant.

- ‘Prior’ medications are medications which started and stopped prior to the first dose of trial medication.
- ‘Concomitant’ medications are medications which:
  - started prior to, on or after the first dose of trial medication or started no later than end of trial medication,
  - AND ended on or after the date of first dose of trial medication or were ongoing at the end of the trial.
- ‘Post’ medications are medications which started after the last dose of trial medication.

In addition all prior (respectively concomitant) prohibited/restricted medications outlined in CTP table 4.2.2.1:1, taken by at least one subject which may significantly impact efficacy assessment as determined by the trial medical advisor will be summarized in tables (overall for the FAS).

## 13. TRIAL MEDICATION EXPOSURE

Exposure to trial medication will be presented for the FAS and SAF.

The proportion of subjects treated at each planned visit (administration every two weeks from Day 1 to Day 337) will be presented.

Descriptive statistics for the number of injections from Day 1 up to Week 48 per subjects will be presented.

Number of subjects per duration of exposure categories, Patient time (years) per duration of exposure, categories and descriptive statistics for duration of exposure will be presented.

Exposure categories will be the following:  $\geq 1$  day,  $\geq 2$  weeks,  $\geq 4$  weeks,  $\geq 12$  weeks,  $\geq 24$  weeks, ,  $\geq 52$  weeks.

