#### 4.1.4 Drug assignment and administration of doses for each patient

Each patient will receive up to 25 SC drug injections (40 mg/0.8 mL) of BI 695501 during the treatment period.

Prefilled syringes will be used for the injections (see [Section 4.1.1](#)). Injections will be administered subcutaneously.

At the Screening visit (Week 48 visit of Trial 1297.2), trial medication will be administered by a suitably qualified, designated trial personnel. This will be the last administration of trial

medication in Trial 1297.2. Detailed training and instruction on self-administration will be provided to the patient at this visit and a self-administration guide will be provided to the patient. Patients will be instructed to accurately record the dates and times of BI 695501 dosing, and the occurrence of any AEs and use of concomitant medications, on the provided diary cards between the ambulatory visits.

The first administration of trial medication in this extension trial will be at the Baseline visit (Day 1). After the first injection (Baseline, Day 1), the patient will remain at the clinical site for at least 1 hour for observation of any AEs.

All subsequent injections of BI 695501 will be administered by the patients themselves, these injections may be performed at the site or at the patients home, as specified in the [Flow Chart](#).

At each visit, 1 to 5 syringes will be dispensed to the patient so that patients can continue to self-administer trial medication at home until the next site visit.

Handling and administration of trial medication will be described in detail in the handling instructions, which will be provided in the ISF.

Dose modification is not permitted during this trial. If a patient misses a dose of trial medication, then the dose should be administered as soon as possible. The 2-week regimen for trial medication administration should resume from the time the dose is administered. In the event of an anaphylactic or other serious allergic reaction, the administration of trial medication will be discontinued immediately, and appropriate therapy instituted.

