### 13.1. DERIVATIONS

The date of first and last trial medication administration will be taken from the eCRF “Self-Administration of trial medication” page. Interruptions, compliance, and dose changes are not taken into account for duration of exposure.

**Duration of exposure (weeks)** = (date of last injection - date of first injection + 1)/ 7.

**Duration of exposure (days)** = (date of last injection - date of first injection + 1).

---

Document: \\ieedc-nas01a\BIOSdata\Boehringer\_Ingelheim\BI\_695501\NVA96235\Biostatistics\Documentation\SAP\10  
v1.0\BI\_1297.3\_SAP\_22JUN2016\_v1.0

Author: Version Number: 1.0  
Version Date: 22JUN2016

Template No: CS\_TP\_BS016 – Revision 3  
Effective Date: 01May2012

Reference: CS\_WI\_BS005

---

Patient Year Exposure (year) = cumulative duration of exposure in days per subjects / 365.25

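### Does the ≥52-week exposure category need correcting when planned dosing ends at Week 48?

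*SAP*

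**What the plan says.** SAP section 13 plans an exposure table for the FAS and SAF. It asks for "Number of subjects per duration of exposure categories, Patient time (years) per duration of exposure", and lists the bounds after the words "Exposure categories will be the following": ≥1 day, then ≥2, ≥4, ≥12 and ≥24 weeks, a blank between two commas, and ≥52 weeks. The same section asks for the proportion treated at each planned visit ("administration every two weeks from Day 1 to Day 337"), for descriptive statistics on the number of injections, and for descriptive statistics on duration.

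Section 13.1 gives duration in weeks as "date of last injection - date of first injection + 1)/ 7", with dates taken from this trial's self-administration eCRF page. It adds that "Interruptions, compliance, and dose changes are not taken into account for duration of exposure".

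On the dosing side, protocol section 4.1.4 states: "Each patient will receive up to 25 SC drug injections (40 mg/0.8 mL) of BI 695501 during the treatment period". For a missed dose the same section says: "The 2-week regimen for trial medication administration should resume from the time the dose is administered". Protocol section 6.1 allows ±2 days at Visit 9 (Week 48) and ±2 days on the two-weekly dosing. The Flow Chart ends trial medication at Visit 9.

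SAP section 9 includes "Completed treatment" among the disposition counts. SAP section 8 leaves the format and content of the tables to templates that are not part of the public documents.

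**The concern.** A trial with 48 weeks of dosing has no natural use for a 52-week exposure row, so the list looks carried over from somewhere else. The trial exists to give long-term safety data, and the exposure table is where a reader looks first to see how many patients had the full planned course and how much patient time they contributed. With the top row out of reach and no printed category at 48 weeks, the table could leave the ≥24-week row as the highest one with patients in it. That row would hold both those who stopped soon after Week 24 and those who finished.

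**Working it through.** **Inputs.** Injections: at most 25, two weeks apart (protocol 4.1.4). First and last planned days: 1 and 337 (SAP 13). Visit 9 window: ±2 days (protocol 6.1). Duration: last date minus first date plus 1, divided by 7 for weeks (SAP 13.1). Study days count from the first dose in this trial (SAP 6.1).

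**Reproducing the plan's schedule.** Last injection day = 1 + (25 − 1) × 14 = 337. Protocol and SAP agree.

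**Exposure for a patient dosed on schedule.**

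| Last injection | Days | Weeks |
|---|---|---|
| Day 335 (early edge of window) | 335 | 335/7 = 47.86 |
| Day 337 (planned) | 337 | 337/7 = 48.14 |
| Day 339 (late edge of window) | 339 | 339/7 = 48.43 |

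If Baseline fell a day early and Visit 9 were still counted from the nominal Day 1, the maximum would be 340 days, or 48.57 weeks.

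**Distance to the top row.** 52 × 7 = 364 days. 364 − 337 = 27 days after the planned last injection, and 364 − 339 = 25 days after the window closes. At exact 14-day spacing, the 26th injection gives 351 days (50.14 weeks) and the 27th gives 365 days (52.14 weeks), against a cap of 25.

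**Other readings of duration.** Adding a closing 14-day dosing interval gives 351/7 = 50.14 weeks, still short. Adding the 70-day residual effect period gives 407/7 = 58.14 weeks, which would reach the row. Section 13.1 does not add it, whereas section 16.1.1.2 adds 70 days explicitly for time at risk.

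**How the row could fill.** Only the first and last dates count, so drift lengthens exposure. With 25 injections, 364 days needs a mean interval of 363/24 = 15.1 days, about 1.1 days longer than planned. A missed dose that restarts the cycle, or the ±2-day dosing tolerance if it accumulates, could produce that. If every one of the 24 intervals ran to 16 days, exposure would be 1 + 24 × 16 = 385 days (55.0 weeks). Either route puts the last injection at least 25 days outside the Visit 9 window.

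**What depends on the row.** The primary endpoint is a proportion of the SAF. Incidence rates under SAP 16.1.1.2 use time to first event or, without an event, time to 70 days after end of treatment. Efficacy uses the FAS at Week 48. None refers to the exposure categories.

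**The case for a change.** The best case for a change is that it is cheap and that one figure is not reported elsewhere. It would take one line of SAP text and one table shell, using dates already collected. The proportion treated at Day 337 and the count of treatment completers show how many finished. No output named in the SAP text, however, gives patient-years among fully exposed patients, and SAP 13 does promise patient time by category. If nothing stands in the blank slot, the ≥24-week row runs from 168 days to about 339 days with no cut between.

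The description of the row is right. The loss is small, for three reasons.

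- Patients whose last injection falls inside the Visit 9 window have 335 to 339 days each. That is 335/365.25 = 0.917 to 339/365.25 = 0.928 patient-years. Their total therefore follows from their number to within 339/335 − 1 = 1.2%.
- The doubled comma is what a dropped entry looks like. If a category near 48 weeks stood there, the complaint about pooling disappears.
- The table templates are not visible, so the final layout cannot be judged from this one line.

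The row is also not impossible under the SAP's formula. The missed-dose rule allows overrun, and a row that shows whether any patient ran that late is odd but does no harm.

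**Conclusion.** No change is needed. The ≥52-week bound sits 27 days beyond the planned last injection, and the expected count is 0 of the anticipated 300 to 400 patients. That expectation assumes dosing close to schedule and exposure measured from first to last injection, as section 13.1 says. A zero there is correct, and no one reading it beside the Day 337 proportion, the duration statistics and the disposition counts would be misled about how many patients completed. No endpoint, incidence rate or denominator moves. The point is a clerical one about a descriptive table. Whether a category is missing between 24 and 52 weeks cannot be settled from the public copy. If none is missing, the cost is a coarser table, not a wrong result.
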